2.6.3 Handling of missing values

For the analysis of secondary efficacy variables 1 and 7-20, the MMRM implicitly imputes missing data under a missing at random assumption.

For the analysis of secondary efficacy variables 4 – 6 and 23, participants with missing data will be imputed using “non-responder” (i.e., “negative” outcome) imputation.

For the analysis of secondary efficacy variables 2, 3, 21 and 22, missing data will not be imputed.

2.6.4 Sensitivity analyses

Not applicable.

2.6.5 Supplementary analyses

Secondary efficacy variables 2 and 3 will be analyzed using MMRM similar to the analysis of primary efficacy variable 1 and secondary efficacy variable 1, respectively. A linear combination of the estimated means will be used to estimate the time-adjusted percent change and absolute change from baseline in LDL-C, where “time-adjusted” refers to the estimated average from Day 90 through Day 330. Least-squares mean of each treatment group, least-squares mean treatment difference, 95% confidence interval for the treatment difference, and p-value based on the fitted model will be reported.

Secondary efficacy variables 4 – 6 will be analyzed similar to the supplementary analysis of primary efficacy variable 2 based on observed data only.

2.6.6 Subgroup analyses

The analysis for secondary efficacy variable 1 (absolute change from baseline in LDL-C) will be repeated for subgroups of participants according to the subgroup categories defined in Section 2.2.1. To this end, the same approach as defined in Section 2.6.2 for the analysis of secondary efficacy variable 1 will be applied separately to the sets of participants within each subgroup category. Note that results for a subgroup category will only be presented if the total across both treatment groups within the category is at least 10 participants.

2.7 Safety analyses

All safety analyses will be performed on the Safety Set.

2.7.1 Adverse events (AEs)

The Medical Dictionary for Regulatory Activities (MedDRA) dictionary will be used for coding AEs, and up-versioning will be applied during the course of study. The final MedDRA version used in this study will be v27.0. Partially missing AE dates will be imputed following Appendix 5.1.2. An AE (classified as preferred term) occurring during the treatment period will be counted as a treatment-emergent AE (TEAE) either if it is not present at Day 1 before treatment or if it is present before treatment but increased in severity during the treatment period. Therefore, all recorded AEs with onset on or after the study treatment start date will be counted as TEAE. In case the AE date values do not allow unequivocally allocating an AE record to TEAE or non-TEAE, the AE will be considered as TEAE in the statistical analysis. The following summary tables will be presented:

- Overall Summary of TEAEs
- TEAEs by System Organ Class (SOC) and Preferred Term (PT)
- TEAEs by PT
- Common ($\geq 3\%$ within either treatment group) by PT
- TEAEs by SOC, PT, and Severity
- TEAEs by SOC, PT, and Relationship to Study Treatment
- Related TEAEs by SOC, PT, and Severity
- Treatment Emergent Serious AEs (TESAEs) by SOC and PT
- TESAEs by PT
- TESAEs by SOC, PT, and Severity
- TESAEs by SOC, PT, and Relationship to Study Treatment
- Related TESAEs by SOC, PT, and Severity
- TEAEs Leading to Withdrawal of Study Treatment by SOC and PT
- TEAEs with a Fatal Outcome by SOC and PT

If more than one event occurred with the same PT for the same participant, the participant will be counted only once for that PT using the most severe or related occurrence for the summary by severity, or relationship to study drug, respectively.

Missing severity and relationship will not be imputed and will be identified as 'missing' in the tables.

For common (3% within either treatment group) TEAEs, serious TEAEs and TEAEs leading to withdrawal of study treatment, risk ratios along with 95% confidence intervals will be presented to compare treatment groups with respect to risk.

For tables presented by SOC and PT, system organ classes are sorted alphabetically and within each system organ class, the preferred terms are sorted in descending order of total frequency.

For tables presented by PT, preferred terms are sorted in descending order of total frequency.

Listings will be presented for participants with SAEs and AEs leading to discontinuation of study treatment.

2.7.1.1 Adverse events of special interest / grouping of AEs

TESAEs and TEAEs of special interest will be tabulated.

SAEs of special interest include:

1. Hepatotoxicity
2. Renal events

AEs of special interest include:

1. TEAE at the injection site
 - TEAE identified as being an AE at the injection site on the AE CRF page
 - Injection site reaction (HLT)
2. Hepatotoxicity
 - Drug related hepatic disorders - comprehensive search (SMQ, broad and narrow)
3. Renal events
 - Acute renal failure (SMQ, broad and narrow)
4. New-onset/worsening of diabetes
 - Hyperglycemia/new-onset diabetes mellitus (SMQ, narrow)
 - Diabetic Complications (HLGT)
 - Diabetes Mellitus (HLT)
 - Carbohydrate tolerance analyses (HLT), excluding PT "Blood glucose decreased"
5. Hypersensitivity
 - Hypersensitivity (SMQ, broad and narrow) excluding
 - PTs 'infusion site %' (e.g., 'infusion site dermatitis', 'infusion site eczema', 'infusion site hypersensitivity', 'infusion site rash', 'infusion site urticaria', 'infusion site vasculitis) and
 - PTs 'injection site %' (e.g., 'injection site dermatitis', 'injection site eczema', 'injection site hypersensitivity', 'injection site rash', 'injection site urticaria' and 'injection site vasculitis')

TEAEs at the injection sites will be presented for all participants and then by baseline glycemic status, specifically for participants with diabetes at baseline and for participants without diabetes at baseline (i.e., participants with pre-diabetes or normoglycemia). The definition of baseline glycemic status is provided in [Table 2-4](#).

2.7.2 Deaths

Listings will be presented for participants with SAEs/AEs leading to a death.

2.7.3 Laboratory data

Laboratory values will be summarized by treatment group, including the observed value, changes and percent changes from baseline at each analysis visit (including Day 330/Last Visit).

Estimated glomerular filtration rate (eGFR) in mL/min/1.73m² will be derived using the Modification of Diet in Renal Disease approach according to the following formula based on serum creatinine values in mg/dL (Levey et al. 2006):

$$\text{eGFR} = 175 \times \text{Serum Cr}^{-1.154} \times \text{Age}^{-0.203} \times 1.212 \text{ (if participant is black)} \times 0.742 \text{ (if female).}$$

Fasting glucose parameter, when used in any analysis, will require the lab sample to be taken while fasting. Glucose values recorded under non-fasting conditions will not be used. For all safety analyses, baseline fasting glucose uses the **average of the last two assessments** measured under fasting conditions at or prior to baseline. If only one fasting glucose value is available at or prior to baseline, the analysis will be based on the available data.

A shift analysis using the normal range (except for eGFR and HbA1c) will be done which counts the number of participants with a low, normal or high value at baseline and a low, normal or high value post baseline.

The following ranges will be used for eGFR and hemoglobin A1c (HbA1c):

- For eGFR, the categories will be Severe = <30 mL/min/1.73m²; Moderate = ≥ 30 to <60 mL/min/1.73m²; Mild = ≥ 60 to <90 mL/min/1.73m²; and Normal = ≥90 mL/min/1.73m².
- For HbA1c, the categories will be ≤5.6%, ≥5.7% to ≤6.4%, and ≥6.5%.

The baseline and worst post-baseline value will be utilized for the shift tables. Note that the shift table dealing with the fasting glucose parameter will require the lab sample to be taken while fasting. Samples taken while the participant was not fasting will not be analyzed. For CSR purposes, HbA1c will be reported under clinical chemistry, not hematology.

New onset or worsening of diabetes during the study will be identified by evaluating different components: 1) adverse events, 2) laboratory measures of either fasting glucose or glycated hemoglobin (HbA1c) and 3) initiation of antidiabetic medication. New onset or worsening of diabetes is defined if ANY of the following conditions are met post-baseline:

- Laboratory results indicating diabetes, which can be any of the following:
 - The participant has HbA1c ≥6.5% on two consecutive tests.

Normoglycemia	Participants with normal glucose control status at baseline are those with ALL of the following: 
• No medical history of diabetes recorded on ACS medical history CRF (diabetes not recorded as “Yes”).• No anti-diabetic medication (ATC level 2 code: A10) at baseline.• HbA1c $< 5.7\%$ AND fasting glucose < 100 mg/dL at baseline. 
Note: Both baseline HbA1c and baseline fasting glucose have to be non-missing to evaluate this category.

The number and percentage of participants with potentially clinically significant (PCS) laboratory values or clinically significant (CS) laboratory values (refer to [Appendix 5.3.2](#) for the criteria) will be summarized. It is possible that some laboratory values for a parameter may be classified as PCS while others are CS. In this case, the CS laboratory value for that parameter will be used in the summaries. For AST, ALT and CK, the most severe result for each subject will be used. For creatinine, the CS criterion will additionally be broken down into the following three mutually exclusive categories:

1. Subjects with baseline value ≤ 2 mg/dL and any post-baseline value > 2 mg/dL.
2. Subjects with baseline value ≤ 2 mg/dL and any post-baseline $\geq 50\%$ change from baseline but no post-baseline value > 2 mg/dL.
3. Subjects with baseline value > 2 mg/dL and any post-baseline $\geq 50\%$ change from baseline.

For liver chemistry parameters (ALT, AST, ALP, TBIL), the number and percentage of subjects whose PCS/CS value returned to baseline level at the last measurement will also be summarized. Here the baseline level is defined as a value of the same category as the baseline category or a value of a better category than the baseline. For example, if a subject's baseline ALT is >3 and ≤ 5 x ULN and the subject's ALT elevated to >5 and ≤ 10 x ULN at the worst measurement post baseline, the subject is considered to have returned to baseline level at the last measurement if the last ALT value of that subject is ≤ 5 x ULN.

Listings of all subjects with PCS or CS laboratory values will be presented. Subjects will appear once per lab parameter but may appear under multiple lab parameters.

The number and percentage of participants satisfying Hy's Law will also be tabulated by treatment group based on the following lab findings:

- Any elevated post-baseline aminotransferases defined as:
 - ALT > 3 x ULN or
 - AST > 3 x ULN
- Elevated post-baseline serum total bilirubin (TBL) > 2 x ULN and serum alkaline phosphatase (ALP) levels < 2 x ULN

Participants must meet all of the criteria listed above at the same time point and have normal lab variables (ALT, AST, TBL) at baseline to be considered a Hy's Law case. The same analysis will be performed excluding the normal baseline value requirement.

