16.2 Appendix 2: Liver event and laboratory trigger definitions & follow-up requirements

Table 16-3 Liver event and laboratory trigger definitions

	Definition/ threshold	
Liver laboratory triggers	ALT or AST > 5 × ULN	
If ALT, AST and total bilirubin normal at baseline:	ALP > 2 × ULN (in the absence of known bone pathology)	
	Total bilirubin > 3 × ULN (in the absence of known Gilbert syndrome)	
	ALT or AST > 3 × ULN and INR > 1.5	
	 Potential Hy's Law cases (defined as ALT or AST > 3 × ULN and Total bilirubin > 2 × ULN [mainly conjugated fraction] without notable increase in ALP to > 2 × ULN) 	
	Any clinical event of jaundice (or equivalent term)	
	ALT or AST > 3 × ULN accompanied by (general) malaise, fatigue, abdominal pain, nausea, or vomiting, or rash with eosinophilia	
	Any adverse event potentially indicative of a liver toxicity*	
If ALT or AST abnormal at baseline:	ALT or AST > 2x baseline or > 300 U/L (whichever occurs first)	

^{*}These events cover the following: hepatic failure, fibrosis and cirrhosis, and other liver damage-related conditions; non-infectious hepatitis; benign, malignant and unspecified liver neoplasms ULN: upper limit of normal

Table 16-4 Follow up requirements for liver laboratory triggers with liver symptoms

ALT or AST	TBL	Liver Symptoms	Action
ALT or AST increase v	vithout bilirubin increase) :	
If normal at baseline: ALT or AST > 3 x ULN	Normal For patients with		No change to study treatment
	Gilbert's syndrome: No change in baseline		Measure ALT,
If elevated at baseline:	TBL		AST, ALP, GGT, TBL, direct and
ALT or AST > 2 x baseline		None	indirect bilirubin, PT/INR, albumin, CK, and
or > 300 U/L (whichever occurs			GLDH in 48-72 hours.
first)			Follow-up for symptoms.

ALT or AST	TBL	Liver Symptoms	Action
If normal at baseline: ALT or AST > 5 x ULN for more than two weeks If elevated at baseline: ALT or AST > 3 x baseline or > 300 U/L (whichever occurs first) for more than two weeks	Normal For patients with Gilbert's syndrome: No change in baseline TBL	None	 Interrupt study drug Measure ALT, AST, ALP, GGT, TBL, direct and indirect
If normal at baseline: ALT or AST > 8 x ULN	Normal	None	bilirubin, PT/INR, albumin, CK, and GLDH in 48-72
ALT or AST increase with bilirubin increase:			hours.
If normal at baseline: ALT or AST > 3 x ULN	TBL > 2 x ULN (or INR > 1.5) For patients with		Follow-up for symptoms.

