If elevated at baseline: ALT or AST > 2 x baseline or > 300 U/L (whichever occurs first)	Gilbert's syndrome: Doubling of direct bilirubin	None	 Initiate close monitoring and workup for competing etiologies. Study drug can be restarted only if
If normal at baseline: ALT or AST > 3 x ULN			another etiology is identified and liver enzymes return to
If elevated at baseline: ALT or AST > 2 x baseline or > 300 U/L (whichever occurs first)	Normal or elevated	Severe fatigue, nausea, vomiting, right upper quadrant pain	baseline.

Table 16-5 Follow up requirements for liver laboratory triggers

Criteria	Actions required	Follow-up monitoring
Total Bilirubin (isolated)		
>1.5 – 3.0 ULN	Maintain treatmentRepeat LFTs within 48-72 hours	Monitor LFTs weekly until resolution ^a to ≤ Grade 1 or to baseline
> 3 - 10 × ULN (in the absence of known Gilbert syndrome)	 Interrupt treatment Repeat LFT within 48-72 hours 	Monitor LFTs weekly until resolution ^a to ≤ Grade 1 or to baseline (ALT, AST, total bilirubin, Albumin, PT/INR, ALP and GGT)

Criteria	Actions required	Follow-up monitoring
	Hospitalize if clinically appropriate	Test for hemolysis (e.g., reticulocytes, haptoglobin, unconjugated [indirect]
	Establish causality	unconjugated [indirect] bilirubin)
	Record the AE and contributing factors (e.g., conmeds, med hx, lab) in the appropriate CRF	,
> 10 x ULN	Discontinue the study treatment immediately	ALT, AST, total bilirubin, Albumin, PT/INR, ALP and
	Hospitalize the participant	GGT until resolution ^c (frequency at investigator
	Establish causality	discretion)
	Record the AE and contributing factors(e.g., conmeds, med hx, lab) in the appropriate CRF	
Any AE potentially indicative of a liver toxicity*	Consider study treatment interruption or discontinuation	Investigator discretion
	Hospitalization if clinically appropriate	
	Establish causality	
	Record the AE and contributing factors(e.g., conmeds, med hx, lab) in the appropriate CRF	

^aResolution is defined as an outcome of one of the following: (1) return to baseline values, (2) stable values at three subsequent monitoring visits at least 2 weeks apart, (3) remain at elevated level after a maximum of 6 months, (4) liver transplantation, and (5) death.

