 2. Subjects with baseline value $\leq 2 \text{ mg/dL}$ and any post-baseline $\geq 50\%$ change from baseline but no post-baseline value $> 2 \text{ mg/dL}$.
 3. Subjects with baseline value $> 2 \text{ mg/dL}$ and any post-baseline $\geq 50\%$ change from baseline.

Table 5-1 Laboratory Test Criteria

Variable	Unit	Lower Boundary	Upper Boundary
Hematology			
Hematocrit	%	$\leq 0.8 \times \text{LLN}$	N/A
Hemoglobin	g/dL	$\leq 10 \text{ g/dL}$	N/A
Platelet Count	$10^9/\text{L}$	$\leq 75^*$	$\geq 700^*$
White Blood Cell Count	$10^9/\text{L}$	≤ 2.8	≥ 16

Variable	Unit	Lower Boundary	Upper Boundary
Serum Chemistry			
Alanine Aminotransferase (ALT/SGPT)	U/L	N/A	>1 and $\leq 3 \times$ ULN
Alanine Aminotransferase (ALT/SGPT)	U/L	N/A	>3 and $\leq 5 \times$ ULN*
Alanine Aminotransferase (ALT/SGPT)	U/L	N/A	>5 and $\leq 10 \times$ ULN*
Alanine Aminotransferase (ALT/SGPT)	U/L	N/A	>10 and $\leq 20 \times$ ULN*
Alanine Aminotransferase (ALT/SGPT)	U/L	N/A	>20 \times ULN*
Alkaline Phosphatase	U/L	N/A	>2 \times ULN*
Aspartate Aminotransferase (AST/SGOT)	U/L	N/A	>1 and $\leq 3 \times$ ULN
Aspartate Aminotransferase (AST/SGOT)	U/L	N/A	>3 and $\leq 5 \times$ ULN*
Aspartate Aminotransferase (AST/SGOT)	U/L	N/A	>5 and $\leq 10 \times$ ULN*
Aspartate Aminotransferase (AST/SGOT)	U/L	N/A	>10 and $\leq 20 \times$ ULN*
Aspartate Aminotransferase (AST/SGOT)	U/L	N/A	>20 \times ULN*
Creatine Kinase (CK)	U/L	N/A	>1 and $\leq 3 \times$ ULN
Creatine Kinase (CK)	U/L	N/A	>3 and $\leq 5 \times$ ULN
Creatine Kinase (CK)	U/L	N/A	>5 \times and $\leq 10 \times$ ULN*
Creatine Kinase (CK)	U/L	N/A	>10 and $\leq 20 \times$ ULN*
Creatine Kinase (CK)	U/L	N/A	>20 \times ULN*
Hemoglobin A1C	%	N/A	$\geq 6.5\%$ and $\geq 0.5\%$ change from baseline
Serum Creatinine	mg/dL	N/A	$\geq 50\%$ increase from baseline or >2 mg/dL*
Total Bilirubin	mg/dL	N/A	>2 \times ULN*

LLN: Lower limit of the standard reference (normal) range; ULN: Upper limit of the standard reference (normal) range; N/A is Not Applicable.

For AST, ALT, and CK, the most severe result for each subject will be used.

*Clinically significant laboratory boundaries. All others are potentially clinically significant.

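### The SAP judges return to baseline level of liver tests by broad category: for ALP and bilirubin the individual baseline plays no part, and for mildly raised ALT/AST a value still above a protocol trigger can count as returned.

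*SAP*

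**What the plan says.** SAP section 2.7.3 plans a row for ALT, AST, ALP and total bilirubin in which "the number and percentage of subjects whose PCS/CS value returned to baseline level at the last measurement will also be summarized". The next sentence gives the rule: "baseline level is defined as a value of the same category as the baseline category", or of a better category. A worked example follows. A participant with baseline ALT above 3 and up to 5x ULN, and a worst value above 5 and up to 10x ULN, is "considered to have returned to baseline level at the last measurement if the last ALT value of that subject is" at or below 5x ULN.

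The categories are those of SAP Table 5-1, where an asterisk marks "Clinically significant laboratory boundaries. All others are potentially clinically significant". ALT and AST have cuts at 1, 3, 5, 10 and 20x ULN. ALP and total bilirubin have one cut each, above 2x ULN. SAP section 5.3.2 admits a participant only if a post-baseline value meets a threshold that the baseline value did not meet.

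Protocol Appendix 2 works with values as well as bands:

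- Table 16-3, under "If ALT or AST abnormal at baseline", sets a trigger at more than 2x baseline or more than 300 U/L. Its triggers for ALP and total bilirubin are above 2x and above 3x ULN.
- Table 16-5 places isolated bilirubin above 1.5 and up to 3.0x ULN under the instruction "Monitor LFTs weekly until resolution", completed in the same cell as resolution to Grade 1 or lower, or to baseline. Footnote a lists five outcomes that count as resolution, the first being "1) return to baseline values".

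**The concern.** The row is there to show whether liver signals reversed, by arm. A reader of the study report will take return to baseline level to mean that the value came back to about where that participant started. With one cut for ALP and bilirubin, the row says only that the last value is no longer above 2x ULN. For ALT and AST, a band from 1 to 3x ULN lets a participant who began just above normal end at nearly three times baseline and still be counted.

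The category rule can only add participants to the returned count, compared with a rule based on the participant's own value. No other planned summary table corrects this at participant level. Shift tables use the worst post-baseline value, by-visit summaries are at group level, and the Hy's Law tables count occurrence. Listings of participants with notable values are planned, but the SAP does not say that they set the last value against baseline.

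**Working it through.** All values are multiples of ULN. Write b for baseline and l for the last value.

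**Rule as coded.** A participant enters if the worst value is in a higher Table 5-1 category than b. The participant has returned if the category of l is no higher than that of b. The SAP does not name the category below the lowest cut. I read it as implied: at or below 1 for ALT/AST, at or below 2 for ALP and bilirubin.

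**The SAP's own example.** With b in (3, 5] and the worst value in (5, 10], the rule gives returned exactly when l ≤ 5. This agrees with the SAP.

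**ALP and bilirubin.** Entry needs b ≤ 2 and a peak above 2. Return needs l ≤ 2. The value of b drops out.

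**ALT and AST, band above 1 to 3.** The trigger for an abnormal baseline is still met when l > 2b. A return needs l ≤ 3. Both can hold only if 2b < 3, so b < 1.5. With b > 1, the ratio l/b stays below 3/1 = 3.

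**Higher bands.** The largest ratio within a band is below 5/3 = 1.67, 10/5 = 2 and 20/10 = 2, so l > 2b cannot occur there.

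**The 300 U/L limb.** The documents give no ULN. In the band up to 3x ULN this limb needs a ULN above 300/3 = 100 U/L. For an assumed ULN of 30 to 60 U/L, 3x ULN is 90 to 180 U/L, so the limb is not reached.

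**Worked values.** The value rule in the last column counts a return if l is at most the larger of 1 (the ULN) and b.

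| Test | b | Peak | l | l/b | SAP category rule | Over 2x an abnormal ALT/AST baseline? | Value rule |
|---|---|---|---|---|---|---|---|
| Bilirubin | 0.6 | 2.4 | 1.9 | 3.2 | returned | – | not returned |
| Bilirubin | 0.5 | 3.2 | 2.0 | 4.0 | returned | – | not returned |
| ALP | 0.5 | 2.6 | 2.0 | 4.0 | returned | – | not returned |
| ALP | 0.5 | 2.6 | 2.01 | 4.0 | not returned | – | not returned |
| ALT | 1.1 | 6 | 2.9 | 2.6 | returned | yes (2.9 > 2.2) | not returned |
| ALT | 1.2 | 3.5 | 3.0 | 2.5 | returned | yes (3.0 > 2.4) | not returned |
| ALT | 1.5 | 4 | 3.0 | 2.0 | returned | no (3.0 is not above 3.0) | not returned |
| ALT | 3.1 | 8 | 5.0 | 1.6 | returned | no (5.0 < 6.2) | not returned |
| ALT | 0.6 | 3.5 | 2.0 | 3.3 | not returned | – | not returned |
| ALT | 0.6 | 3.5 | 1.0 | 1.7 | returned | – | returned |

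**Set against the protocol.** A bilirubin ending above 1.5 and up to 2x ULN counts as returned in the SAP while it lies inside the weekly-monitoring band of Table 16-5. A returned ALP or bilirubin is at most 2x ULN, so it cannot exceed the Table 16-3 triggers for those tests.

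**Where baselines will lie.** Exclusion criterion 16 removes participants with confirmed ALT or AST above 3x ULN at screening. Raised baselines will therefore fall mostly in the 1 to 3 band. The SAP's example, with a baseline above 3x ULN, illustrates a case that should be rare here.

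**The case against.** The strongest defence is that entry to the row is by category, so exit by the same categories is symmetric. The SAP also states its definition openly and gives an example. That is fair as far as it goes: the rule is a disclosed convention and is applied consistently. It does not justify the label for ALP and bilirubin, where the individual baseline has no influence on the result.

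The protocol does not insist on exact values either. A reader might infer from footnote a of Table 16-5 that resolution there means return to baseline values and nothing else. The documents do not support that. The same table accepts Grade 1 or lower, and the footnote also allows stable values at three visits, persistent elevation after at most 6 months, transplantation and death. Those entries guide follow-up of isolated bilirubin and of liver adverse events and do not define a report table. The documents also give no numerical limit for Grade 1. What stands is narrower: a value can lie in the monitored band and be tabulated as returned.

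A value rule has its own rough edges. With a normal baseline, bilirubin ending at 1.0x ULN from 0.3x ULN counts as returned at 3.3 times baseline. With a raised baseline, ALT of 1.50 ending at 1.51x ULN does not count. This is a reason to show both counts rather than to keep only the category count.

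By-visit summaries, the Hy's Law tables, the listings and the hepatotoxicity event tables are unaffected, so liver signals themselves are not hidden.

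**Conclusion.** The point holds within limits. For ALP and total bilirubin, the row reports only that the last value is at or below 2x ULN. For ALT and AST, the conflict with the Table 16-3 trigger is confined to baselines above 1 and below 1.5x ULN with a last value above twice baseline and at most 3x ULN.

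Three stronger readings are tempting and not supported:

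- It does not follow that participants above a Table 16-3 trigger are counted as returned for all four tests. For ALP and bilirubin that is impossible.
- It does not follow that ALT or AST normal at baseline and ending at twice ULN counts as returned. Such a participant must come back to 1x ULN or below.
- It does not follow that everyone with a normal baseline is misreported. Only those who first crossed a threshold enter the row.

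The number affected cannot be computed from the documents and is probably small. No test, alpha, sample size or stopping rule depends on the row. Even so, the bias has one direction, and this is the only planned summary table of reversibility at participant level. The conclusion rests on reading values below the lowest cut as one category.

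**What to change.** In SAP section 2.7.3, rename the existing row as return to baseline category. Beside it, for ALT, AST, ALP and total bilirubin, add the number and percentage whose last measurement is no higher than the larger of the ULN and the participant's own baseline value. The denominator can stay as planned. Adding a further ALP and bilirubin category alone would not be enough, because it leaves the ALT/AST case untouched.

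The cost is a sentence or two in the SAP and minor programming from data already collected. The recovery percentage by the value rule will be somewhat less favourable. That rule is strict for small fluctuations just above a raised baseline, which is why both rows should be shown.
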